1.13. Assessment variables:**1.13.1. Main**

The primary endpoint of the study will be the proportion of patients who continue to have a viral load <37 copies/mL at 24 weeks using an intention-to-treat analysis.

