6.1 Primary and Secondary Endpoints**Primary Endpoint:**

The primary endpoint of the study will be the proportion of patients who continue to have a standard plasma viral load (<37 copies/mL) at 24 weeks by intention-to-treat analysis.

Secondary endpoints:

- 1) The proportion of patients with ultrasensitive viral load (<1 copy/mL) after 24 weeks.
- 2) The change from baseline to 24 weeks in the viral reservoir of peripheral blood mononuclear cells
- 3) Changes from baseline to 24 weeks in TREC production, immune profile of activation (CD38 and HLA-DR) and senescence (CD57 and CD28) in CD4 and CD8 lineages, in naïve and effector and memory T cell ratios (CCR7 and CD45RA), and changes in apoptosis levels in vitro by annexin V staining.
- 4) Changes in plasma levels of efavirenz.
- 5) Changes in sleep quality (Pittsburgh Sleep Quality Index), plasma levels of vitamin D and lipids, and estimated glomerular filtration rate.
- 6) Overall safety (reporting side effects, serious side effects, and discontinuation of treatment due to side effects)

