6.2 Design

Although the hypothesis of the study has been based on various congruent information that allow us to face with sufficient guarantee the feasibility of the study and the eventual demonstration of the virological and immunological efficacy of the ATRIPLA® dose reduction strategy, we are not absolutely certain that an unacceptably high virological failure rate (standard viral load ≥ 37 copies/mL on two consecutive occasions) can occur in the arm

experimental. We will consider a priori that the failure of at least 20% (n=6) of the patients in the experimental arm will represent an unacceptably high virological failure rate. In this case, its conclusion will be considered premature. In this extreme case, the data of the patients already included up to the time of the premature conclusion of the study would be analyzed.

The present study is proposed as a proof of concept to be able to formulate another study with a sufficiently large sample size to adequately demonstrate the non-inferiority of the strategy. The results of the present study can help to design the non-inferiority study and to estimate its sample size.

STUDY PROCEDURES

Selection Evaluations								
Clinical Evaluations		Selection						
Informed consent								X
Inclusion and exclusion criteria								X
Assignment of the selection code								X
Vital signs								X
Weight Determination								X
Height determination								X
Demographics								X
Medical history								X
Physical examination								X
Concomitant medications								X
Confirmation of the use of contraceptive methods by the patient and his or her partner								X

Clinical Evaluations	Basal Day 0	S 1 (#)	S 2 (#)	S 4 (#)	S 6 (#)	S 8 (#)	S 12	S 24
Meet Inclusion and Exclusion Criteria	X							
Signed Informed Consent	X							
Vital signs	X							
Weight	X							X
Physical examination	X						X	X
Adverse events		X	X	X	X	X	X	X
Concomitant medications	X	X	X	X	X	X	X	X
Simplified Compliance Questionnaire		X	X	X	X	X	X	X
Test sobre calidad del sueño (Pittsburgh Sleep Quality Index)	X							X
Haematology	X							X
Blood biochemistry	X							X

Clinical Evaluations	Basal Day 0	S 1 (#)	S 2 (#)	S 4 (#)	S 6 (#)	S 8 (#)	S 12	S 24
Standard plasma viral load	X	X	X	X	X	X	X	X
Ultrasensitive plasma viral load (\$)	X							X
HIV-1 reservoir of PBMCs	X							X
Immunology (CD4/CD8)	X						X	X
Immunology Sample	X							X
Pregnancy test (women only) Y(&)	X	X	X	X	X	X	X	X
Pharmacokinetics	X							X

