7.3 Withdrawal criteria (endpoints)

Treatment with the study drug will be terminated **immediately** during the study for any of the following reasons:

- Patient with virologic failure
- Pregnancy during the study.
- Express wish of the patient
- Medical criteria
- Exitus

Treatment with the study drug **may** be terminated during the study for any of the following reasons:

- The medical investigator determines that a SAE is possibly or likely related to the study drug.
- Failure to administer, evaluate, or other study requirements.

8. Treatment of Subjects

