11.2 Sample size

11.3 Analysis

Comparison of patient proportions will be performed using Fisher's exact test and the 95% confidence interval will be calculated for the difference in proportions.

Quantitative data at baseline and after 24 weeks, as well as absolute and relative changes at 24 weeks, will be compared using the Wilcoxon rank sum test. The point estimate and 95% confidence interval of the difference in medians will be estimated using the Hodges-Lehman methodology using the Moses free distribution.

Correlations between continuous variables will be evaluated using Spearman's rank correlation test.

The study of baseline predictors of response will be carried out by means of a multivariate analysis of multiple logistic regression.

Limitations of the study:

Although the hypothesis of the study has been based on various congruent information that allow us to face with sufficient guarantee the feasibility of the study and the eventual demonstration of the virological and immunological efficacy of the ATRIPLA® dose reduction strategy, we are not absolutely certain that an unacceptably high virological failure rate (standard viral load ≥ 37 copies/mL on two consecutive occasions) may occur in the experimental arm. We will consider a priori that the failure of at least 20% (n=6) of the patients in the experimental arm will represent an unacceptably high virological failure rate. In this case, its conclusion will be considered premature. In this extreme case, the data of the patients already included would be analyzed.

This study, even with the most favorable virologic and immunological results, would not constitute definitive proof of the safety and efficacy of ATRIPLA®'s dose reduction strategy. The present study is only a proof of concept and another study with a sufficiently large sample size would be needed to adequately demonstrate the non-inferiority of the strategy. The results of the present study can help to design the non-inferiority study and to estimate its sample size.

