11.5 Processing of lost data

Missing data imputation techniques will not be used. Only the available data will be analyzed.

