11.6 Deviations from the statistical plan

Any deviation from the planned statistical analyses will be justified and detailed in the reports derived from the processing of the data.

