11.7 Population under analysis

The population analyzed in the study will consist of all patients included in the study as detailed in the protocol and without major deviations from the protocol.

12. Direct Access to Source Data/Documents

The sponsor shall ensure that it is specified in the protocol or other written agreement that the investigator or institution shall allow direct access to the source data or documents for monitoring, auditing and review by the IRB as well as inspection of the trial by the competent health authorities.

13. Ethics

General considerations: The test will be carried out in accordance with the principles emanating from the Declaration of Helsinki (See Annex *VIII*) and according to the legal regulations in force (Royal Decree 223/2004) and will not be started until the approval of the reference IRB has been obtained, the

approval of the Management of all participating centres, and authorisation from the Spanish Agency for Medicines and Health Products.

Information to the subjects: Patients will be informed orally and in writing and all relevant information adapted to their level of understanding will be communicated to the participants.
(See *Attachment III: Patient Information Sheet/Written Consent Sheet*)

14. Data Management and Records Archiving

The patient will be informed that their participation in the trial will be treated with the same confidentiality as their clinical documentation.

In the data collection notebook, the patient will be identified only by their inclusion code in the study.

The patient's name will not appear in any publication or communication of the results of the study.

The patient's participation in the trial will be reflected in their medical history.

The investigator will complete a list that will include the names of the patients participating in the trial, their inclusion number in the trial and their medical history.

Only researchers and data quality assurance and data analysis personnel will have access to the participant's clinical documentation. Eventually, persons duly authorised by the Sponsor and the Health Authorities and the Clinical Research Ethics Committee may audit or inspect the trial. Personal information will not be available to the public, in compliance with the provisions of Organic Law 15/1999, of 13 December, on the Protection of Personal Data.

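### Section 11.7 restricts the analysed population to patients without major deviations, which contradicts the intention-to-treat primary endpoint

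*Combined protocol and SAP*

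**What the plan says.** The primary endpoint is defined twice, each time with its analysis principle attached. The synopsis (1.13.1) takes the proportion with "viral load <37 copies/mL at 24 weeks using an intention-to-treat analysis". Section 6.1 repeats it as "standard plasma viral load (<37 copies/mL) at 24 weeks by intention-to-treat analysis".

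The statistics section defines one population, in 11.7: "all patients included in the study as detailed in the protocol and without major deviations from the protocol". It defines no separate intention-to-treat or per-protocol set. Section 11.3 names Fisher's exact test and a 95% confidence interval for the difference in proportions, but assigns no population to either.

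Two neighbouring rules bear on the point. Section 11.5 says: "Missing data imputation techniques will not be used. Only the available data will be analyzed". Section 11.6 says: "Any deviation from the planned statistical analyses will be justified and detailed in the reports derived from the processing of the data".

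**The concern.** Removing randomised patients because of what happened after randomisation is not intention-to-treat. An analyst who follows 11.7 and one who follows 6.1 would use different denominators, and both could claim to have followed the protocol. Because "major" has no definition and no stated time of classification, the choice could be made after the viral loads are known.

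Three features of this trial make that more than a formality.

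- It is open-label, and Section 7.3 lists "Failure to administer, evaluate, or other study requirements" among the reasons for which treatment may be stopped. Deviations after randomisation are thus foreseen as a possibility.
- The arms are observed unequally. The compliance questionnaire is scheduled at weeks 1, 2, 4, 6, 8, 12 and 24 in the experimental arm, but only at weeks 12 and 24 in the control arm. Deviations have seven occasions to be recorded in one arm and two in the other.
- The estimate is meant to be used later. Section 11.3 states: "The results of the present study can help to design the non-inferiority study and to estimate its sample size". The suppression proportions are the obvious input.

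**Working it through.** **Arm size.** Section 6.2 states: "failure of at least 20% (n=6) of the patients in the experimental arm will represent an unacceptably high virological failure rate". Hence n = 6/0.20 = 30 in the experimental arm. With 60 patients in total (11.1), 30 remain for control. The plan has no sample size calculation to reproduce.

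**The texts side by side.**

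| Section | Population implied for the primary endpoint |
|---|---|
| 1.13.1, 6.1 | All randomised patients (intention-to-treat) |
| 11.3 | None named |
| 11.5 | Patients with a week-24 value |
| 11.6 | None; departures from the plan must be justified |
| 11.7 | Patients without major deviations, no endpoint exempted |

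The first and last rows cannot both hold once any randomised patient has a major deviation.

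**Size of the effect.** The documents give no deviation rate, so all success counts and exclusions below are assumptions. Differences are experimental minus control.

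For x successes in n, with p = x/n and z = 1.96, the Wilson limits (l, u) are [p + z²/2n ± z√(p(1−p)/n + z²/4n²)]/(1 + z²/n). With index 1 for experimental and 2 for control, the Newcombe interval for d = p₁ − p₂ runs from d − √[(p₁−l₁)² + (u₂−p₂)²] to d + √[(u₁−p₁)² + (p₂−l₂)²]. P-values are two-sided Fisher.

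Base case, nobody excluded: 26/30 = 86.7% (Wilson 70.3 to 94.7) against 29/30 = 96.7% (83.3 to 99.4).

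- d = −10.0 points
- lower limit = −10.0 − √(16.4² + 2.7²) = −26.6
- upper limit = −10.0 + √(8.0² + 13.4²) = +5.6

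Shift from excluding one experimental patient:

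- one failure: 26/29 − 26/30 = +3.0 points
- one suppressed patient: 25/29 − 26/30 = −0.5 points

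| Excluded under 11.7 | Exp. | Control | Difference (95% CI), points | p |
|---|---|---|---|---|
| None | 26/30 | 29/30 | −10.0 (−26.6 to +5.6) | 0.35 |
| Exp.: 3 failing | 26/27 | 29/30 | −0.4 (−15.2 to +13.3) | 1.00 |
| Exp.: 1 failing, 2 suppressed | 24/27 | 29/30 | −7.8 (−24.9 to +7.4) | 0.34 |
| Exp.: 3 suppressed | 23/27 | 29/30 | −11.5 (−29.4 to +4.6) | 0.18 |
| Control: the 1 failing | 26/30 | 29/29 | −13.3 (−29.7 to +0.9) | 0.11 |
| Exp.: 1 failing, 2 suppressed; control: 3 suppressed | 24/27 | 26/27 | −7.4 (−24.6 to +8.9) | 0.61 |

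The estimate moves in either direction, depending on who deviates. The test stays non-significant throughout this table, but that is not general. With control at 30/30:

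| Non-suppressed experimental patients excluded | Exp. | Difference, points | p |
|---|---|---|---|
| 0 of 6 | 24/30 | −20.0 (−37.3 to −4.5) | 0.024 |
| 2 of 6 | 24/28 | −14.3 | 0.048 |
| 3 of 6 | 24/27 | −11.1 | 0.100 |
| 4 of 6 | 24/26 | −7.7 (−24.1 to +4.9) | 0.211 |

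The six non-suppressed patients need not all be confirmed virologic failures, so this case need not reach the premature-conclusion threshold.

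**Section 11.5.** Suppose 2 of the 4 base-case non-successes are missing week-24 values. Available data give 26/28 = 92.9%; counting missing as failure gives 26/30 = 86.7%. This is an unsettled denominator, not a second contradiction.

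**The case against.** The best reply is that the specific rule governs. Intention-to-treat is stated twice within the definition of the primary endpoint, whereas 11.7 is one general sentence that names no endpoint. On that reading 11.7 applies only to the other analyses, and 11.6 would stop a silent switch. The reading is reasonable, which is why the text permits a per-protocol primary result and does not prescribe one. But the plan does not say so: 11.7 speaks of the population of the whole study, and 11.6 protects the planned analysis without settling which population is planned.

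A second reply is that little depends on it. This is a proof of concept with no margin and no sample size calculation, and it disclaims definitive proof. The threshold of six confirmed failures is a count during the trial and is not obviously affected by 11.7. That limits the damage to the reported estimate, its comparison and their use in planning the next trial.

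A third is that the mechanism is inferred. Section 7.3 describes a contingency about stopping treatment; it neither predicts deviations nor calls stopping a major deviation. Virologic failure is itself a protocol event, so excluding a failing patient requires a separate major deviation. More visits need not produce more major deviations. The significance reversal also needs a selected configuration, with at least three of six non-suppressed patients excluded. All of this stands as caution about likelihood. It does not remove the conflict between the sections.

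**Conclusion.** The concern holds and must be fixed: followed literally, 11.7 yields a primary result that is not intention-to-treat, and no section resolves the conflict. This conclusion rests on the text alone.

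The size is illustrative. It assumes 30 per arm, implied by the plan, and hypothetical success and exclusion counts. From a base of −10.0 points, three experimental exclusions move the difference anywhere from −0.4 to −11.5, and excluding the single control failure moves it to −13.3. Whether any such shift occurs depends on deviations that the documents do not quantify. The missing-data ambiguity in 11.5 is secondary and does not carry the conclusion.

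**What to change.** Reword 11.7 along these lines: for the primary endpoint, the analysis population is all randomised patients, analysed in the arm assigned, regardless of protocol deviations; the set without major deviations is a secondary per-protocol sensitivity analysis. Define "major" before the analysis. If 11.7 was meant only for the secondary endpoints, one sentence there saying so would resolve the contradiction.

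In 11.5, state how a missing week-24 viral load counts for the primary endpoint. Missing = failure, with available data as a sensitivity analysis, is one option. Classifying deviations without sight of the viral loads would be a useful extra, but the contradiction can be removed without it.

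The cost is edits to two sections, one definition and one sensitivity table. The reported suppression rate may be less favourable, because missing = failure also counts patients who miss week 24 for unrelated reasons. For example, if 2 otherwise suppressed patients are missing, the rate is 24/30 = 80.0% where available data would give 24/28 = 85.7%.
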